2 BACKGROUND

2.1 Lung Cancer: A Major Public Health and Clinical Challenge

The incidence and prevalence of lung cancer has risen dramatically. In 1953, primary lung cancer became the most common cause of cancer death in men, while the same occurred for women in 1985 in the United States.¹ Worldwide, lung cancer is one of the most commonly diagnosed cancer types and also the leading cause of death in men.¹ Among the most aggressive cancers, lung cancer causes more deaths than the next three most lethal common cancers combined.¹ The lungs are the most common site for metastatic disease (secondary lung cancers), which are identified in 30-55% of metastatic cancer patients.²

Non-small cell lung cancer (NSCLC) accounts for the majority of primary lung cancer (~85%). Stage I disease (small lesion, no spread in lymph nodes) and stage II disease (larger lesion, no spread in lymph nodes, and involvement of structures such as the chest wall or diaphragm, or involvement of hilar lymph nodes) make up about a third of patients with

NSCLC.¹ Treatment options for lung cancer depend on histology, stage, and patient-specific factors. Randomized clinical trials have established surgical resection of a single lobe of the lung, or lobectomy, as the treatment of choice for operable lung cancer patients in stage I and II,¹ improving survival to up to 75%.^{1,2} For those patients with stage IIIa disease (involvement of ipsilateral mediastinal lymph nodes), surgical resection plays a role after chemoradiation therapy, provided no further spread of disease has occurred, and patients remain medically operable. The lung is also a common site for metastatic spread from other primary cancers (most common: breast, colon, sarcoma, and melanoma). Experience with surgical resection of secondary lung cancers (pulmonary metastasectomy), once the primary cancer has been controlled, has confirmed that resection can substantially prolong survival and potentially cure some patients.³⁻⁸ In 2015, lung cancer accounted for \$13.4 billion in costs out of a total expense of cancer care of \$147.5 billion.⁹ Lung cancer patients often experience multidimensional impairments affecting quality-of-life (QoL) during their course of disease.¹⁰ Impairments result from both symptoms of the disease and comorbidities, as well as side effects of treatment. Interventions aimed at minimizing morbidity would have a significant impact on public and population health.

2.2 Functional Outcomes after Surgery

Surgical resection is the treatment of choice for primary lung cancer patients with stage I to IIIa lung cancer, as it offers the best chance for cure. The goal of surgical resection for lung cancer patients is excision of one or more lobes of the lung that are affected by cancer. For secondary lung cancers, this goal is complete removal of the lesion with adequate margins. Lung cancer patients suffer substantial functional decline and reduced activity levels following surgical lung resection.¹¹⁻¹³ There is a significant deterioration in six minute walk (6MW) distance at five days post-operatively compared with pre-operatively (average of 337m vs. 467m).¹¹ Lung resection is associated with an immediate 12% reduction in exercise tolerance and 18% reduction in pulmonary function.¹² Lung resection also has an impact on post-surgery health-related QoL¹⁴⁻¹⁶ and causes persistent pain following surgical treatment for up to 33% of patients.¹⁷ The postsurgical period is associated with a 20-40% reduction in physiological and functional capacity, particularly in the elderly with comorbidities, who may never return to pre-surgery levels of function.¹⁸⁻²⁰ Additionally, poor pre-surgery physical performance has been shown to increase the risk of mortality,²¹ post-surgery complications, and prolonged functional recovery.²² Thus, the pre-operative and post-operative periods are ideal periods to intervene. Enhancing functional capacity 2-4 weeks prior to a lung resection is feasible and motivates the patient to continue with physical activities and exercises postoperatively, which is essential for optimizing outcomes

2.3 Exercise Training in Oncological Patients

Exercise intervention studies prior to, during, and after cancer treatment consistently show beneficial effects for various physical and psychosocial outcomes.²³⁻³³ The American College of Sports Medicine Roundtable on Exercise Guidelines for Cancer Survivors concluded that exercise training is safe during and after cancer treatments and results in improved physical function, QoL, and cancer-related fatigue in multiple cancer survivor

groups.²⁴ It has been shown that exercise interventions can ameliorate or reverse cancer treatment-induced impairment of physical function and QoL, such as cancer-related fatigue and pain.²⁴⁻³⁷

Several non-randomized intervention studies and ten randomized controlled trials have demonstrated positive effects of pre- or post-surgical exercise intervention in lung cancer patients.^{11,38-59} In a review, Crandall et al. concluded that compared to usual care, exercise interventions among lung cancer patients both pre- and post-surgery are associated with improved cardiopulmonary exercise capacity and muscle strength, and reduced fatigue, post-operative complications and hospital length of stay.⁶⁰ Despite this consistent and convincing evidence, implementation of exercise programs in clinical practice for patients with lung cancer is still low, perhaps due to unacceptable financial and resource demands on the patient and the health care system (e.g., center-based exercise). There are further gaps in the evidence base: Although the majority of exercise studies have demonstrated positive impact, only a small Turkish trial has covered the continuum from pre-surgery to the survivorship period,⁴⁹ and none have used a highly standardized, yet patient-tailored approach. Most of the exercise studies in lung cancer patients have been developed outside of the United States, and there are currently only two American trials recruiting patients, both of which differ substantially in their design. One trial tests a 16-week exercise intervention that starts at least one year following the completion of therapy and requires participants to attend three supervised sessions per week (NCT 01068210). The other trial provides mindfulness-based pulmonary rehabilitation prior to surgery for both lung cancer and COPD patients (NCT 01682850). There is clearly a need for testing innovative exercise interventions in lung cancer patients that can be translated into clinical practice across the entire continuum of care.

2.4 Physical Functioning (AM-PAC Scores) Among Lung Cancer Patients at HCI

The AM-PAC mobility score⁶¹ was implemented as the inpatient mobility assessment tool in June of 2014 within the University of Utah Health Care system (UUHS) and has become a standard mobility measure collected by physical therapists in the University's acute hospitals (see Appendices 1-3). The PEP Study team plans to extend assessments to presurgery visits for the standardized precision exercise program. As part of a pilot study, $n = 63$ AM-PAC scores were collected at [name] clinic from lung cancer patients during their pre-operative outpatient clinic visit. The average score was 54 ± 13 . Patients were 54% female, with mean age of 61 ± 15 years. Overall 44% of patients were categorized as AM-PAC stage 3, indicating that they had difficulty with community mobility. Eighteen % had stage 2, indicating that they had difficulty with mobility within the home. Patients ranging across mobility stages 2-4 are generally capable of performing exercise that will have the greatest likelihood in resulting in positive outcomes. The level of physical function of patients in the clinic can vary widely, reinforcing the PEP concept of an exercise intervention that is tailored for the mobility stage of each patient. No correlations between the AM-PAC score and age, sex, or cancer stage (all $p > 0.05$; $|r| < 0.30$); some 75 year olds had better function than 50 year old patients. This suggests that the AM-PAC score is well-

suited and sufficient to assess physical function, and should be evaluated for appropriate tailoring of exercise interventions.

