2.7 PEP Study Pilot

In order to test the feasibility of patient recruitment and study implementation, a pilot study was conducted (IRB 91478, The PEP Study: Precision Exercise Prescription among lung cancer patients, approved 7/3/2016).

Between 7/7/2016 and 10/11/2016, n=18 lung cancer patients were recruited into the intervention program at their pre-surgery consult with [name]. Every eligible patient was approached, and all patients approached (100%) agreed to participate in the intervention. Their physical function was assessed with 6MW test, SPPB, and AM-PAC score. The testing and precise exercise prescription was implemented within normal clinic workflow and clinic space by a trained physical therapist ([name]) using existing space in the clinic of Thoracic Surgery. The intervention included individually-prescribed exercise modes (mobility, flexibility, callisthenic, aerobic, and resistance) and dosages (low, moderate, high) tailored to the patient's AM-PAC mobility stage.

The baseline observed 6MW distance varied from 209-679m with a mean distance of 467 ± 119 m. Normal 6MW distance for healthy 60-69 year olds is 572m for men and 538m for women. For ten patients, post-operative 6MW distances were obtained prior to 10/15 (max. follow-up time 20 post-operative days within the pilot). Compared to comparable control patients (for whom 6MW distances at comparable pre- and post-time points were available) PEP patients maintained their physical function and experienced a lesser reduction in 6MW distance (median 6.8% decline in PEP and 18.7% in controls, see Figure 1). Although this comparison is not based on a randomized study, it is notable that the decrease (47m) in 6MW distance in the controls exceeded the minimal clinically important distance, despite the time points achieved at this point being very early in the intervention process. To date, only one patient has dropped out (5.5% drop-out rate).

A follow-up phone evaluation of the PEP intervention showed that patients planned to exercise an average of 4.7 days per week and 93% agreed (86% strongly) that exercise should be part of their cancer treatment; 86% also strongly agreed with the statement that they believe that the exercise program will have a positive effect on their cancer treatment. Several patients noted that they loved being in the program and the effort of our team. They emphasized that the exercise intervention helped them immensely with recovery from surgery.

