In conclusion, these preliminary results demonstrate that: (1) our team has successfully worked together on the PEP study intervention, generated pilot data, and two scientific abstracts;^{90,91} (2) lung cancer patients differ dramatically in their functional status, independent of age, sex, and stage, requiring individualized interventions; (3) the PEP intervention was feasible within the existing workflow of a high-volume surgical clinic, with only the addition of a physical therapist to manage the intervention; (4) the PEP intervention is welcomed by patients and appears to show early efficacy; and (5) our assumptions for anticipated patient recruitment (65%) and drop-out rates (15%) are conservative. Overall, this pilot work sets the base for a successful clinical trial.

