10 STATISTICAL CONSIDERATIONS

10.1 Randomization

Randomization will have a uniform 1:1 allocation ratio with block sizes of 8. The random allocation sequence will be stratified by the mobility staging (high vs. low) provided by the pre-treatment AM-PAC stage and whether it is a primary or secondary lung cancer diagnosis, based on primary data (as described in section 2.4), the AMPAC stage is sufficient to assess physical function.

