10.3 Primary Endpoint Analysis

Analyses will include all patients that are evaluable for our primary endpoint (expected at least $n=150$). The primary outcome will be the group effect for an analysis of covariance model with 6MW test at 2 months post-surgery as outcome and pretreatment 6MW test as covariate, tested at the nominal two-sided 0.05 significance level. A sensitivity analysis will be performed with additional adjustment variables (listed as covariates in Section 10.1). Missing data will be handled using multivariate imputation by chained equations⁸⁸ as implemented in the R package “mice”.

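### The primary ANCOVA leaves age, gender and the two stratification factors out, forgoing a small gain in precision that would cost almost nothing

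*Combined protocol and SAP*

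**What the plan says.** **Primary model.** Section 10.3 specifies an analysis of covariance of 6MW at 2 months after surgery on group and pretreatment 6MW, tested two-sided at 0.05. It then adds: "A sensitivity analysis will be performed with additional adjustment variables". It says these variables are listed in Section 10.1. Section 10.1 names only the two stratification factors, AM-PAC mobility stage (high or low) and primary or secondary lung cancer. The covariate list itself is in 10.2 and includes age, gender, and primary or secondary cancer. AM-PAC stage is not on it.

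**Other endpoints.** Section 10.4 adjusts the main models for the other continuous outcomes for the covariate list (again cited as 10.1) and for baseline values where available. It also plans to look at gender-specific effects.

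**Sex and walking distance.** Section 2.7 gives reference values: "Normal 6MW distance for healthy 60-69 year olds is 572m for men and 538m for women".

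**The AM-PAC statements.** Section 2.4 describes 63 pilot scores ("Patients were 54% female, with mean age of 61") and reports "No correlations between the AM-PAC score and age, sex, or cancer stage (all $p > 0.05$; $|r| < 0.30". It takes this to suggest that the score is sufficient to assess physical function. Section 10.1 repeats the conclusion without the hedge, to support the choice of stratifier: "based on primary data (as described in section 2.4), the AMPAC stage is sufficient to assess physical function". The pilot conclusions in 2.7 go further: "lung cancer patients differ dramatically in their functional status, independent of age, sex, and stage, requiring individualized interventions".

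**The concern.** Age and gender are fixed at baseline, available for every patient (9.3 abstracts both from the medical record), and plausibly related to walking distance. The protocol's own reference values differ by 572 - 538 = 34 m between healthy men and women. Neither variable is balanced by stratification. The plan regards them as worth adjusting for in the main models of its other continuous endpoints, but not in the primary model, and gives no reason for the difference.

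The two stratification factors are also absent from the primary model. If they are prognostic, a model that ignores them gives a standard error slightly larger than the stratified design warrants.

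What is at stake is precision in a trial whose stated inputs give power of only about 80%. The validity of the primary test is not in question.

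The cross-reference adds an ambiguity. Read literally, the sensitivity analysis in 10.3 would adjust for AM-PAC stage and primary or secondary cancer, and not for age or gender. Read as presumably intended, it would adjust for age and gender, and not for AM-PAC stage.

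**Working it through.** **Inputs from the documents (10.2, 10.3):** difference 39.95 m; SD 100 m; correlation 0.5 between repeated 6MW measurements; 200 randomized, 25% dropout, so 200 × 0.75 = 150 evaluable (this reproduces); two-sided alpha 0.05. The plan says power was simulated but its text gives no resulting figure, so there is none to reproduce.

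**1. Power of the model as planned.**
- Residual SD = 100 × √(1 - 0.5²) = 86.6 m; residual variance = 7,500 m².
- SE of the group effect = 86.6 × √(4/150) = 14.14 m.
- 39.95 / 14.14 = 2.82. Power is 80.1% by the t distribution with 147 df, 80.6% by the normal approximation, and 79.8% in a 10,000-run simulation.

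**2. How much could gender explain?** Assume that the 34 m healthy-norm gap carries over to these patients, and take the planned 106 men of 200 (53%). Gender variance = 0.53 × 0.47 = 0.249.
- Nothing absorbed by baseline 6MW: 34² × 0.249 = 288 m²; 288 / 7,500 = 3.8%.
- Same gap at baseline, half removed by the slope of 0.5: 17² × 0.249 = 72 m²; 72 / 7,500 = 1.0%.

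So gender alone would explain about 1-4% of residual variance. The documents give no figure for age; 1-5% for the two together is an assumed range.

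**3. Power with age and gender added** (residual variance × (1 - share); t distribution):

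| Share explained | SE (m) | Power |
|---|---|---|
| 0% | 14.14 | 80.1% |
| 1% | 14.07 | 80.5% |
| 2% | 14.00 | 80.9% |
| 5% | 13.78 | 82.1% |

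Using 143 df in place of 147, to allow for age, gender and two stratification terms, lowers each figure by less than 0.1 percentage point. A 1-5% cut in variance is worth the same as having 150/0.99 = 152 to 150/0.95 = 158 evaluable patients.

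**4. Size of a chance imbalance in gender.** With 75 per arm, the SD of the difference in proportion male is √(0.249 × 4/150) = 8.2 percentage points, so the 95% range is about ±16 points. This moves the estimate by 17 × 0.16 = 2.7 m to 34 × 0.16 = 5.4 m. Across randomizations these shifts average zero and are already reflected in the standard error.

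**5. Type I error.** In 10,000 simulated null trials that omitted a covariate explaining 10% of residual variance, the rejection rate was 4.8%. There is no inflation.

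**6. The pilot correlations (two-sided tests assumed).** With n = 63, p > 0.05 means |r| < 0.248, consistent with the reported bound of 0.30. For sex, 54% of 63 is about 34 women and 29 men. Power to detect a 0.5-SD difference (6.5 AM-PAC points at the reported SD of 13) is 49.5%. An observed r of 0.24 would have a 95% confidence interval of about -0.01 to 0.46. Moderate associations are therefore not excluded.

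**The case against.** The strongest reply is that the plan is already valid. Under 1:1 randomization, a linear ANCOVA that omits a prognostic covariate is unbiased and holds its alpha. Baseline 6MW, probably the most useful single covariate, is in the model, and an adjusted sensitivity analysis is prespecified. The gain may be less than half a percentage point of power, and replacing the primary model in an amended protocol is more than an editorial change. All of this stands, and it keeps the point small. It does not explain why the primary endpoint is treated differently from the other continuous endpoints.

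Three stronger readings do not hold:
- A reader might infer that age and gender were left out because AM-PAC was judged sufficient. No section says so. The AM-PAC inference is used for tailoring exercise (2.4, 2.7) and for choosing a stratifier (10.1). AM-PAC is not in the primary model, so it does not stand in for age or gender there.
- A reader might set the 34 m gap against the 39.95 m target and conclude that gender could nearly account for the planned effect. That compares a difference between persons with a difference between arms. The gap reaches the estimate only in proportion to the imbalance in gender.
- A reader might take the low power of the pilot correlations as the main fault. A well-powered null would not establish sufficiency either; that would need agreement with a performance measure such as 6MW or SPPB.

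**Conclusion.** This is an inexpensive improvement, and the plan is not in error without it. Age, gender and the stratification factors belong in the prespecified primary ANCOVA for precision and for consistency with 10.4. The gain from age and gender is from about 80% power to about 80.5-82%. It rests on the plan's SD of 100 m, correlation of 0.5 and 150 evaluable patients, and on an assumed 1-5% of residual variance explained. The 1-4% for gender alone also assumes that the healthy-norm gap applies to these patients. The contribution of the stratification factors cannot be sized from the documents.

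The wrong cross-reference in 10.3 and 10.4 is a definite defect, because it leaves the content of the adjusted models open.

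The AM-PAC statements claim more than 63 null correlations can show. Correcting them is a matter of wording and changes no analysis.

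**What to change.** Before outcomes are examined by arm:

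1. In 10.3, prespecify the primary ANCOVA with group, pretreatment 6MW, age (continuous), gender, AM-PAC stage (high/low) and primary/secondary cancer. State the high/low cut-off, which neither 10.1 nor Appendix 2 gives.
2. Keep the model with pretreatment 6MW alone as the sensitivity analysis.
3. In 10.3 and 10.4, change the covariate reference from 10.1 to 10.2.
4. As wording only: soften the sufficiency statement in 2.4 and 10.1 and the independence statement in 2.7, or report the pilot correlations with confidence intervals.

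**Cost:** a protocol amendment and four degrees of freedom out of 147, with no new data collection. The gain may be very small if baseline 6MW already carries most of the age and gender effect.

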2.5 Rationale for Conducting the Study

Studies that have investigated the effect of exercise in lung cancer patients undergoing surgery have been center-based and resource intensive, and consequently have not been implemented in the clinical setting.⁶⁵⁻⁶⁷ Pre-operatively, effective exercise programs lasting 6-12 weeks are not feasible since patients with lung cancer do not want to delay surgery. In fact, one randomized controlled trial (RCT)³⁸ was prematurely discontinued because neither patients nor providers were willing to delay surgery longer than 4 weeks. Post-surgery, home-based exercise strategies capable of improving mobility and fatigue levels of patients following surgery for lung cancer and colorectal cancer⁴⁵ have been prohibitively expensive because they required supervised visits by a nurse.³² In addition, these programs have been “one size fits all,” lacking a personalized approach to optimize adherence and efficacy.⁶⁵⁻⁶⁸

To date, no attempt has been made to test a pragmatic and personalized exercise intervention (i.e., face to face visits at clinical contacts, telephone counseling in the home, and personalized exercise prescriptions) before and following surgery for patients with lung cancer. Unfortunately, the application of personalized principles of exercise in randomized controlled trials with cancer survivors (specifically non-breast cancer survivors) is incomplete and inconsistent.⁶⁹ To establish consistency in the exercise prescription while accommodating the exercise to match the patient’s level of mobility, a validated basic mobility assessment tool to create modes and dosages of exercise that can be implemented across the continuum of the pre- and post-operative surgical experience in lung cancer patients may prove to be beneficial. The Activity Measure-Post Acute Care™ (AM-PAC) (described in Figure 2) will be used as the basic mobility assessment tool that prompts the prescribed exercise mode and dose for the patient. The AM-PAC has been developed as a pragmatic measurement system that can be used across care settings and a very broad range of impairments, limitations and diagnoses.⁷⁰ The PEP Study’s approach with the use of AMPAC will address a gap in the care of lung cancer patients, i.e., the underutilization of exercise because it is clinically not pragmatic and it is not known how and when to implement exercise.⁷¹

2.6 Rationale for the PEP Intervention Design

[name] previous work with the empirically validated MotivAction intervention will serve as the foundation for the PEP intervention, which will be adapted for lung cancer patients. The Health Action Process Approach (HAPA) describes a general framework for self-regulation and behavior change among individuals with chronic illness.⁷²⁻⁷⁸ The overarching conceptual basis is the social cognitive model⁷⁴⁻⁷⁶ which posits that high levels of both motivation and self-efficacy are necessary for behavior change.²⁹ Thus, in the HAPA model, a key element for lasting behavior change is a motivational shift that instigates a decision and commitment to change. In the absence of such a shift, skill training is viewed as premature.^{74,79,80} As such, the PEP intervention focuses on both enhancing the motivation

to achieve and maintain change, as well as developing the self-efficacy and skills necessary to do so. Many interventions focus largely on either motivation or problem-solving/skills training despite the strong theoretical and empirical bases for doing both. When motivation is addressed, the focus is typically on initiating a change attempt, with little attention given to the motivation to maintain change. Specific components of the PEP intervention include: individualized tailoring of the exercise prescription; individualized tailoring of the counseling based on motivation and self-efficacy to engage in exercise including the use of simple motivational interviewing (MI) ⁷⁹ techniques (e.g., reflective listening, avoiding argumentation; developing discrepancy); identifying barriers to exercising and problem-solving solutions; use of goal setting and self-monitoring (including via the activity tracker); and, implementing specific strategies for improving self-efficacy (e.g., building a series of small achievable goals; practicing specific exercises during the face to face visits to increase mastery (see Figure 1).

In sum, the PEP intervention is a directive but patient-centered approach designed to enhance motivation for change, and increase self-efficacy in a non-confrontational manner. Several meta-analyses and systematic reviews have supported the efficacy of both social cognitive and MI-based interventions for behavior change in general and with respect to cancer patients specifically.⁸¹⁻⁸⁵

[figure not shown]

Figure 1: PEP interventions strategies and mechanisms

